9.17 Worsening of Solid Tumor

Worsening and/or progression of the patient's solid tumor should not be recorded as an AE or SAE unless resulted in death within the AE reporting period. These data will be captured as efficacy assessment data only.

9.18 Expedited Reporting Requirements for Serious Adverse Events

9.18.1 Reporting Requirements for Serious Adverse Events

Investigators will submit reports of all SAEs, regardless of attribution, to the sponsor or its designee within 24 hours of learning of the events.

For initial SAE reports, investigators should record all case details that can be gathered on the SAE report form. Relevant follow-up information should be submitted to the sponsor or its designee as soon as it becomes available and/or upon request.

Any life-threatening (ie, imminent risk of death) or fatal AE that is attributed by the investigator to the investigational product will be telephoned to the Medical Monitor immediately, followed by submission of written case details on the SAE report Form within 24 hours.

9.19 Adverse Event Follow-Up Duration

The investigator should follow all unresolved AEs and SAEs until the events are resolved or stabilized, the patient is lost to follow-up, or it has been determined that the study drug or participation is not the cause of the AE/SAE. Resolution of AEs and SAEs (with dates) should be documented on the appropriate AE/SAE CRF and in the patient's medical record to facilitate source data verification (SDV). For SAEs, if, after follow-up, return to baseline status or stabilization cannot be established, an explanation should be recorded in the additional case details section of the Adverse Event CRF.

For some SAEs, additional case details deemed necessary to appropriately evaluate the SAE report (eg, hospital discharge summary, consultant report, or autopsy report) may be followed-up by telephone, fax, email, and/or a monitoring visit to obtain.

9.20 Post-Study Adverse Events

At the last scheduled visit, the investigator should instruct each patient to report to the investigator any subsequent SAEs that the patient's personal physician believes could be related to prior study drug.

The investigator should notify the sponsor or its designee of any death or other SAE occurring at any time after a patient has discontinued or terminated study participation if felt to be related to prior study drug. The sponsor or its designee should also be notified if the investigator should become aware of the development of cancer or of a congenital anomaly in a subsequently conceived offspring of a patient that participated in this study.

10 STATISTICAL ANALYSIS

All statistical analysis will be performed under the direction of Hutchison MediPharma personnel. Any data analysis carried out independently by the investigator should be submitted to Hutchison MediPharma prior to publication or presentation.

The final analysis will be based on patient data collected through study discontinuation or study termination. There is no planned formal interim analysis. However, the accrued data may be analyzed for internal decision-making purposes, for example to provide information for a potential Phase 3 study design.

Final analysis for each cohort will occur once the last patient had been followed for sufficient time for the analysis of primary endpoint. For instance, for Arm A, final analysis will occur when the last patient had been on treatment for at least 16 weeks or discontinued early following discontinuation criteria. Timing of final analyses for cohorts may be combined if they occur close together. Details of the statistical analysis and data reporting will be provided in the Statistical Analysis Plan (SAP) document finalized prior to database lock.

Data will be summarized using descriptive statistics (continuous data) and/or contingency tables (categorical data) for demographic and baseline characteristics, efficacy measurements, safety measurements, and PK measurements. Information regarding compliance with efficacy testing and availability of data will be documented. Graphical techniques (eg, waterfall plots, Kaplan-Meier curves) will be used when such methods are appropriate and informative. The baseline value used in each analysis will be the last (most recent) pre-treatment value. Time to event variables will be summarized descriptively using Kaplan-Meier medians and quartiles. Analyses will be based upon the observed data unless methods for handling missing data are specified. Analyses will be performed using SAS® (Version 9.1 or higher).

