Study Duration	Study duration for patients in the dose escalation is up to approximately 1 year and 2 months, including: 
• Screening period of up to 28 days• Treatment period until disease progression, death, end of study, or early discontinuation as specified in the protocol, or up to 1 year• Dose Completion visit at 30 (± 7) days after the last dose of study drug Study duration for patients in the dose expansion consists of: 
• Screening period of up to 28 days• Treatment period until disease progression, death, end of study, or early discontinuation as specified in the protocol• Dose Completion visit at 30 (± 7) days after the last dose of study drug
Treatment Duration	Treatment duration is: 
• Up to 1 year for patients in the dose escalation phase• Approximately 16 weeks for Arm A• Approximately 11 months for Arms B and C• Approximately 4 months for Arm D
Health Measurement/ Observation	The dose escalation phase will evaluate the safety and tolerability of surufatinib in patients with advanced solid tumors of any type and determine the MTD and/or RP2D by evaluating the incidence of DLT. The expansion phase evaluates the anticancer activity of surufatinib at the RP2D determined in the dose escalation phase as determined from the PFS.
Visit Frequency	All enrolled patients undergo screening, which may be up to 28 days prior to the first dose of study drug. Each treatment cycle is 28 days. Patients are assessed at day 1, day 8 (± 1), day 15 (± 1), and day 22 (± 1) in cycle 1, day 1 and day 15 (± 1) in cycle 2, and then day 1 (± 3) of cycle 3 and all subsequent treatment cycles. Tumor assessments are conducted according to RECIST Version 1.1 criteria at screening, cycle 2 day 1 and every 8 (± 1) weeks thereafter. After receiving the last dose of study drug, patients undergo a Treatment Completion visit at 30 (± 7 days) after receiving the last dose of surufatinib. The safety of all enrolled patients will be closely monitored from the time of the initial dose of investigational treatment until 30 days after the last treatment dose.

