5.5 Patient Discontinuation

All study participants have the right to withdraw from the study at any time.

The investigator has the right to discontinue a patient from the study for any medical condition that the investigator determines may jeopardize the patient's safety if he or she continues in the study and for reasons of non-compliance (eg, missed doses, visits) or pregnancy or if the investigator determines it is in the best interest of the patient.

Any patient who discontinues treatment but does not withdraw informed consent should be encouraged to return to the study site for a treatment completion visit. See [Appendix 1](#) for the assessments that are to be performed for patients who prematurely withdraw from the study during the treatment period. The primary reason for discontinuation must be recorded on the appropriate CRF. Patients discontinuing surufatinib for reasons other than progression of the underlying malignancy are to continue tumor assessments per [Appendix 1](#), until documentation of disease progression, start of new anti-tumor therapy, or withdrawal of informed consent.

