5.4. FINAL ANALYSIS

All final, planned analyses identified in this SAP will be performed by IQVIA Biostatistics by following sponsor's authorization of this SAP and final Database Lock (DBL) for this study.

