16. EFFICACY OUTCOMES

Efficacy data will be summarized by dose cohort in dose escalation phase and by disease cohort in dose expansion phase. PFS and OS will be analyzed for the SAS. The other efficacy variables (BOR, ORR, DCR, TTR, and DOR) will be analyzed for EAS.

Treatment efficacy will be evaluated by using tumor responses which will be assessed and documented at Screening, Day 1 of Cycle 2 and every 8 (+/-1 week) weeks on Day 1 of every other cycles afterwards (i.e. Cycle 4, 6... etc), until the occurrence of progressive disease (PD) according to the standard of Response Evaluation Criteria in Solid Tumors (RECIST) Version 1.1. Confirmation of CR and PR is required at no less than 4-week intervals between the date of initial response/progression and the confirmation assessment date. When the patient interrupts study medication due to AEs or other reasons, the evaluation should be conducted as scheduled. For suspected cases of PD before the start of the next scheduled assessment, additional tumor assessments will be done.

Tumor responses data are captured on CRF page "Tumor Measurement - Target Lesions", "Tumor Assessment - Non-Target lesions", "Tumor Assessment - New Lesions" and "Assessment of Disease". The confirmed best overall response (BOR, refer Section 16.1.2) will be summarized for EAS and will be presented together with summaries for objective response rate (ORR) and disease control rate (DCR).

The baseline sum of diameters will be presented with other baseline characteristics.

Tumor assessments for target lesion, non-target lesion, and new lesion will be presented in a listing. In addition, a listing of overall response including lesion responses, sum of diameters, and the corresponding change from baseline in tumor diameter will be provided.

Tumor assessment performed at the treatment completion visit (details can be found in SAP Section 7.3) is an eligible data point for the derivation of all efficacy endpoints, following the derivation rules described in Section 16.1.

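### Protocol 10's worked example for Arm A (16 weeks on treatment, or early discontinuation) permits a data cut before the first scan after the 16-week landmark, and the SAP sets no later cohort cut-off

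*Protocol*

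**What the plan says.** Protocol 10 gives a general rule: "Final analysis for each cohort will occur once the last patient had been followed for sufficient time for the analysis of primary endpoint". One worked illustration follows, and it concerns the BTC cohort (Arm A) only: "final analysis will occur when the last patient had been on treatment for at least 16 weeks or discontinued early following discontinuation criteria". Arms B, C and D have no stated trigger. The same section adds: "The final analysis will be based on patient data collected through study discontinuation or study termination". It leaves analysis details to the SAP. SAP 5.4 says only that final analyses follow sponsor authorization of the SAP and "final Database Lock (DBL) for this study"; it states no cohort cut-off and no minimum follow-up.

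Tumor assessments are due at screening, at Cycle 2 Day 1 and then "every 8 (+/-1 week) weeks on Day 1 of every other cycles afterwards" (SAP 16). The synopsis states: "Each treatment cycle is 28 days". Protocol 5.5 keeps scans going after drug is stopped: "Patients discontinuing surufatinib for reasons other than progression of the underlying malignancy are to continue tumor assessments", until progression, new therapy or withdrawal of consent.

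SAP 16.1.1 and its Table 1 censor a patient with no event by the cut-off at the last evaluable scan. A death counts on its own date. Progression is dated by the scan that shows it. SAP 16.4 plans no sensitivity analysis.

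**The concern.** The only concrete description of sufficient follow-up falls short of what the SAP's censoring rule needs. Sixteen weeks lies between two scheduled scans. If a cut were made at the stated minimum, the most recently enrolled event-free patients would carry a last scan near week 12 and leave the risk set before the primary time point. Their counterparts who died between weeks 12 and 16 would stay in as events.

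The early-discontinuation limb adds a second gap. A patient dosed near the end of accrual who stops without progression satisfies the trigger at once, although Protocol 5.5 still requires scans. The cut could then come before that patient's week-12 scan, and a progression or death before week 16 could be missed.

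Two things are at stake: the 16-week Kaplan-Meier estimate, and the count of 30 in the 9-of-30 rule. That rule applies to PFS-evaluable patients, a term that Protocol 10.2 does not define.

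**Working it through.** **Inputs from the documents.** 28-day cycles (Protocol synopsis); scan schedule (Protocol 5.1.2, SAP 16); 16-week landmark (Protocol 4.2.2); censoring rules (SAP 16.1.1); 9-of-30 rule (Protocol 10.1). **Not stated, so assumed:** uniform accrual over 26, 52 or 78 weeks; exponential PFS; 15% of events are deaths; where a drug-stop rate is needed, 15.8% by week 16. The last figure is borrowed from the share stopping for TEAEs in Protocol 2.3.

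**1. The plan's own figures.** P(X ≥ 9) = Σ C(30,x) pˣ(1−p)³⁰⁻ˣ for x = 9 to 30. This gives 0.9060 at p = 0.40 and 0.0278 at p = 0.15, matching the stated 90.6% and 2.8%. The Clopper-Pearson 80% lower limits for 9/30 and 10/30 are 19.0% and 21.8%, also as stated.

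**2. Scan calendar.** Day 1 of cycle c is study day 28(c−1)+1.
- C4D1 = Day 85, window 78 to 92.
- C6D1 = Day 141, window 134 to 148.
- Landmark: 16 × 7 = Day 112.
- Gap to the next scan: 134−112 = 22 days to 148−112 = 36 days.

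With a cut 16 weeks after the last first dose, anyone first dosed in the final 22 to 36 days of accrual has no scheduled scan after the landmark. If event-free, that patient is censored at C4D1. Later deaths, and progressions found later in the week-12 scan window, are then divided by a smaller risk set, which lowers the estimate.

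**3. How many, by hand.** Count the last patient plus those of the other 29 dosed in the preceding 4 weeks (midpoint of 3 to 5). Multiply by about 0.49, the share event-free at week 16 as the SAP dates events when the true rate is 40%. That share exceeds 0.40 because progression arising after the week-12 scan is first dated near week 20.
- 26 weeks: (1 + 29×4/26) × 0.49 = 5.46 × 0.49 = 2.7
- 52 weeks: (1 + 29×4/52) × 0.49 = 3.23 × 0.49 = 1.6
- 78 weeks: (1 + 29×4/78) × 0.49 = 2.49 × 0.49 = 1.2

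**4. Simulation of the SAP censoring rule** (n = 30, 1,500 runs per setting, true rate 40%):

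| Accrual (weeks) | Cut at 16 weeks: censored before week 16 | KM at 16 weeks vs full follow-up | Drug stop also satisfies trigger: censored | KM vs full follow-up |
|---|---|---|---|---|
| 26 | 2.70 | 0.464 vs 0.486 (−2.2 points) | 3.27 | 0.461 vs 0.488 (−2.7) |
| 52 | 1.61 | 0.476 vs 0.489 (−1.3) | 2.19 | 0.473 vs 0.488 (−1.5) |
| 78 | 1.20 | 0.482 vs 0.491 (−0.9) | 1.75 | 0.476 vs 0.487 (−1.1) |

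The sampling SD of the estimate is about 9 points. At a true rate of 15%, the 16-week cut censors 1.22, 0.74 and 0.57 patients, with shifts of −1.9, −1.1 and −0.8 points.

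**5. The 9-of-30 rule.** If k censored patients are dropped as not evaluable and the threshold of 9 is kept:

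| n | Power at 40% | False positive rate at 15% |
|---|---|---|
| 30 | 90.6% | 2.8% |
| 29 | 88.1% | 2.2% |
| 28 | 85.2% | 1.8% |
| 27 | 81.6% | 1.4% |

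These treat the dropped patients as a random subset. They are in fact selected for being event-free, so the true loss of power would be larger.

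**6. With a 21-week cut-off** in the same simulation, 0 of 30 patients are administratively censored before week 16, and the Kaplan-Meier value equals that with full follow-up.

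**The case against.** The strongest reply is that the 16-week sentence is an illustration and a floor, governed by the rule just before it that follow-up must be sufficient for the primary endpoint. Protocol 10 also bases the final analysis on data through study discontinuation or termination, and SAP 5.4 ties it to a study-level lock. SAP 16.3.2 plans survival probabilities out to 11 months in BTC and STS, which sits poorly with a week-16 cut. All of this stands: the early cut is allowed, not prescribed. What remains is that no text rules it out.

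Four stronger readings are tempting, and the documents do not support them.
- *Stopping drug ends PFS data collection.* It does not. Protocol 5.5 continues scans, SAP 16 counts the treatment-completion scan, and SAP 16.1.1 has no censoring at drug stop. The exclusion of scans after end of treatment in SAP 5.2 applies to the past interim analysis only. Early stoppers enrolled well before the last patient can still reach the landmark.
- *Patients without a C6D1 scan pass as progression-free by default.* Progression first seen at C6D1 is dated after week 16, so such a patient is progression-free at the landmark either way.
- *One early stop by the last-enrolled patient fires the trigger for everyone.* In the simulation this would censor 2.7 to 6.5 of 30 patients and shift the estimate by up to about 4 points. It conflicts with the sufficient-follow-up rule.
- *Every arm has this trigger.* Only Arm A's is written down. The gap in Arms B to D arises only if the same convention is used there.

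**Conclusion.** The point holds in a limited form. The stated minimum permits an Arm A cut before C6D1, and before late-enrolled patients who stopped drug without progression reach week 16. SAP 16.1.1 would then censor recent event-free patients near week 12. The bias is downward and small: about 1 to 3 of 30 patients, and about 1 to 3 points at 16 weeks. Those sizes rest on assumed accrual, share of deaths and drug-stop rate, none of which the documents give for this trial. The 9-of-30 rule is more exposed than the Kaplan-Meier estimate, because it depends on an undefined evaluable count. There is no formal hypothesis test, so the harm lies in precision and interpretation. The change is worth making because it is cheap and removes administrative censoring ahead of the primary time point.

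**What to change.** In Protocol 10, and repeated in SAP 5.4, state that the data cut-off for a cohort's final analysis is no earlier than the close of the first scheduled scan window after the landmark, counted from first dose of the last-dosed patient:
- Arms A and D: C6D1 plus 1 week, about 21 weeks.
- Arms B and C: C14D1 plus 1 week, about 53 weeks.

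An earlier cut is allowed only if every patient short of that point has progressed, died, started new anti-tumor therapy, withdrawn consent or been lost to follow-up. Stopping surufatinib alone does not satisfy the trigger. Define PFS-evaluable in the same edit.

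Cost: wording in two documents and a later readout. In Arm A the delay is at most 148−112 = 36 days, about 5 weeks, beyond the current minimum. Had the other arms been cut at their landmarks, it would be about 26 days in Arm D (148−121.75) and 37 days in Arms B and C (372−334.8). It is shorter if all open patients resolve sooner. No extra patients or scans are needed.

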10.1 Determination of Sample Size

The total number of patients enrolled will depend on the number of dose escalations and the need to further characterize individual cohorts in the expansion phase.

The planned enrollment for this study is approximately 95 to 150 patients, including 35 patients in the dose escalation phase, and approximately 115 patients for the dose expansion phase. Dose expansion phase will enroll patients in specific disease cohorts, 30 patients in the BTC Arm, at least 15 patients each in the pNET and epNET arms, and 55 patients in the STS arm (10 patients with LMS, 10 patients with UPS, 10 patients with epithelioid sarcoma, 10 patients with angiosarcoma, 10 patients with SS, and 5 patients with PVNS).

Sample size for Arm A: BTC cohort in dose expansion phase:

The PFS rate at 16 weeks was selected as the primary endpoint for the expansion phase of the study in patients with BTC. The PFS rate at 16 weeks is defined as the percent of patients without evidence of disease progression or death after 16 weeks on study among the PFS-evaluable patients.

For a BTC cohort with at least 30 evaluable patients, the treatment effect may be considered positive if there are at least 9 evaluable patients without evidence of progression or death after 16 weeks on study. This event will occur with probabilities 90.6% (true positive

rate) if the true PFS rate at 16 weeks is 40%, and 2.8% (false positive rate) if the true PFS rate at 16 weeks is 15%.

In addition, for a cohort with 30 evaluable patients, if 9 (30.0%) patients, or 10 (33.3%) patients without progression or death at 16 weeks are observed, then the lower limit of the 80% two-sided CIs for PFS rate at 16 weeks would be 19.0% and 21.8%, respectively.

Sample size for Arm B: pNET cohort in dose expansion phase:

For a pNET cohort with at least 15 evaluable patients, the treatment effect may be considered positive if there are at least 6 evaluable patients without evidence of disease progression or death after 11 months on study. This event will occur with probabilities 84.9% (true positive rate) if the true PFS rate at 11 months is 50%, and 4.9% (false positive rate) if the true PFS rate at 11 months is 19%.

In addition, for a cohort with 15 evaluable patients, if the 6 (40%) patients or 7 (47%) patients without progression or death at 11 months are observed, the lower limit of the 80% two-sided CIs for PFS rate at 11 months would be 22.6% and 28.2%, respectively.

Sample size for Arm C: epNET cohort in dose expansion phase:

For a pNET cohort with at least 15 evaluable patients, the treatment effect may be considered positive if there are at least 6 evaluable patients without evidence of disease progression or death after 11 months on study. This event will occur with probabilities 84.9% (true positive rate) if the true PFS rate at 11 months is 50%, and 4.9% (false positive rate) if the true PFS rate at 11 months is 19%.

In addition, for a cohort with 15 evaluable patients, if the 6 (40%) patients or 7 (47%) patients without progression or death at 11 months are observed, the lower limit of the 80% two-sided CIs for PFS rate at 11 months would be 22.6% and 28.2%, respectively.

Sample size for Arm D: STS cohort in dose expansion phase:

Arm D will consist of 6 cohorts of STS subtypes. The LMS, UPS, epitheloid sarcoma, angiosarcoma, and SS cohorts will enroll at least 10 evaluable patients each. The treatment effect may be considered positive if there are at least 3 evaluable patients in each cohort without evidence of disease progression or death after 4 months on study. This event will occur with probabilities of 83.3% (true positive rate) if the true PFS rate at 4 months is 40%, and 7% (false positive rate) if the true PFS rate at 4 months is 10%.

For the PVNS cohort, it is planned to enroll 5 evaluable patients. This sample size is based on feasibility.

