This is a dose escalation and dose expansion study, which is conducted in a US patient population to confirm the safety and efficacy results of clinical studies performed in China. During the dose expansion portion of the study, 4 expansion cohorts have been added, Arm A (BTC cohort), Arm B (pNET cohort), Arm C (epNET cohort), and Arm D (STS). Preliminary data from the cohort of patients with advanced BTC in the Expansion Cohort of the present study have shown encouraging results. In order to characterize further the safety and efficacy of surufatinib in this patient population, an additional 15 patients will be enrolled into Arm A (BTC) of the expansion phase, for a total enrollment of at least 30 patients. Arm B (pNET) and Arm C (epNET) will enroll no less than 15 patients each. If needed, Arm B and Arm C could also enroll additional patients to characterize further the safety and efficacy of surufatinib in these patient populations. Arm D (STS) will enroll approximately 55 patients.

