5.2 Sample Size

Approximately 95 to 150 patients will be enrolled in this two-phase study: 35 patients in the dose escalation phase and approximately 115 additional patients in the dose expansion phase. The actual enrollment number may vary, depending on the number of dose levels evaluated and the number of DLTs observed in each cohort, as well as the potential need to further characterize individual cohorts in the dose expansion phase.

As of Amendment 7, an additional 15 patients will be enrolled into Arm A (BTC) of the Expansion phase, for a total enrollment of at least 30 advanced BTC patients. The reason for increasing enrollment into Arm A (advanced BTC) is that preliminary data from the ongoing patients in this cohort have shown encouraging results. The additional patients will allow further characterization of the safety and efficacy of surufatinib in this patient population. Arm B (pNET) and Arm C (epNET) will enroll at least 15 patients each. If needed, Arm B and Arm C could enroll additional patients in order to characterize further the safety and efficacy of surufatinib in these patient populations.

As of Amendment 8, approximately 45 additional patients with STS will be enrolled to Arm D.

As of Amendment 10, an additional 10 patients will be added to the arm D (STS) for a total enrollment of 55 patients.

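### The positive rule for the pNET and epNET arms fixes a count of 6 for 15 or more evaluable patients, but its quoted rates (84.9% and 4.9%) hold only at exactly 15

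*Protocol*

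**What the plan says.** Protocol 10.1 gives each expansion cohort a count at which the treatment effect may be called positive. For Arm B: "For a pNET cohort with at least 15 evaluable patients, the treatment effect may be considered positive if there are at least 6 evaluable patients" are free of progression or death at 11 months. The Arm C paragraph repeats this rule under the epNET heading (it still says pNET, which looks like a copying slip and does not affect the arithmetic). Both quote 84.9% and 4.9% for true 11-month rates of 50% and 19%. The interval sentence that follows is tied to a cohort of 15, without the open end: "the lower limit of the 80% two-sided CIs for PFS rate at 11 months would be 22.6% and 28.2%, respectively".

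The other arms use the same form:
- Arm A: "For a BTC cohort with at least 30 evaluable patients, the treatment effect may be considered positive if there are at least 9 evaluable patients" are free of progression or death at 16 weeks, with 90.6% and 2.8% quoted for true rates of 40% and 15%.
- Arm D: five subtype "cohorts will enroll at least 10 evaluable patients each", and "The treatment effect may be considered positive if there are at least 3 evaluable patients in each cohort" are free of progression or death at 4 months, with 83.3% and 7% quoted for 40% and 10%. The PVNS cohort of 5 has no rule.

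On size, Protocol 3.2 says "Arm B (pNET) and Arm C (epNET) will enroll no less than 15 patients each", and 10.1 plans "30 patients in the BTC Arm, at least 15 patients each in the pNET and epNET arms". Protocol 5.2 adds "If needed, Arm B and Arm C could enroll additional patients", and SAP 4.2 repeats that permission. No section changes the count when a cohort exceeds its minimum. SAP 4.2 refers back to Protocol 10.1 for the sample-size detail.

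**The concern.** A fixed count gets easier to reach as the cohort grows. Six of 15 is 40.0%; six of 18 is 33.3%. One pair of rates cannot describe a rule whose denominator is open upwards, yet 10.1 quotes one pair for every size from 15 up.

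The sizes at issue are permitted ones. Arms B and C may take extra patients. Separately, SAP section 6 pools escalation-phase patients of the same tumour type treated at the recommended dose with the expansion cohort, and no section says whether they count towards the six.

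These rates are the only operating characteristics the protocol gives for its cohort sizes. A report that called an enlarged NET cohort positive and cited 4.9% would understate the chance of that call under an inactive drug.

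**Working it through.** **Inputs**, all from Protocol 10.1: minimum evaluable number n, count r, lower rate p0, higher rate p1.
- NET (Arms B and C): n = 15, r = 6, p0 = 19%, p1 = 50%
- BTC (Arm A): n = 30, r = 9, p0 = 15%, p1 = 40%
- Each of five STS subtypes: n = 10, r = 3, p0 = 10%, p1 = 40%

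**Formula.** With landmark status known for every patient, the number progression-free is binomial, and P(positive) = P(X ≥ r | n, p) = 1 − Σ C(n,k) p^k (1−p)^(n−k), summed over k = 0 to r−1. Setting p = p0 gives the false-positive rate; p = p1 gives the true-positive rate.

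**Step 1: reproduce the protocol.**
- NET, P(X ≥ 6 | 15): 4.90% and 84.91% (printed 4.9% and 84.9%)
- BTC, P(X ≥ 9 | 30): 2.78% and 90.60% (printed 2.8% and 90.6%)
- STS subtype, P(X ≥ 3 | 10): 7.02% and 83.27% (printed 7% and 83.3%)

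All six figures reproduce at the minimum n.

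**Step 2: keep the NET count at 6 and let n grow.** Sizes above 15 are illustrative; the documents give no expected excess.

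| n | proportion required | false positive at 19% | true positive at 50% |
|---|---|---|---|
| 15 | 40.0% | 4.9% | 84.9% |
| 16 | 37.5% | 6.6% | 89.5% |
| 17 | 35.3% | 8.6% | 92.8% |
| 18 | 33.3% | 11.0% | 95.2% |
| 20 | 30.0% | 16.4% | 97.9% |

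One extra patient moves both rates off the printed values. Three extra more than double the false-positive rate (11.0 / 4.9 ≈ 2.2).

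**Step 3: the same for the other arms, one extra patient.**
- BTC, count 9: false positive 2.8% at n = 30, 3.4% at n = 31 (+0.6 points)
- STS subtype, count 3: 7.0% at n = 10, 9.0% at n = 11 (+2.0 points)
- NET, for comparison: 4.9% to 6.6% (+1.7 points)

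Per added patient, an STS subtype therefore drifts at least as fast as a NET arm in absolute points. What sets Arms B and C apart is the explicit permission to add patients.

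**Step 4: a count rescaled to the actual n.** Take the smallest r whose false-positive rate does not exceed the value at the minimum n.
- NET: 7 for n = 16–18, 8 for n = 19–22
- BTC: 10 for n = 31–34, 11 for n = 35–39
- STS subtype: 4 for n = 11–16

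Power dips just above the minimum. NET has 77.3% at n = 16, 83.4% at 17, 88.1% at 18 and 82.0% at 19, against 84.9% at 15. BTC has 85.7% at n = 31, and an STS subtype 70.4% at n = 11.

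**The case against.** The strongest reply is that enlarged cohorts are not the plan. Protocol 10.1 envisages about 115 expansion patients, and 30 + 15 + 15 + 55 = 115, so each NET arm is planned at 15, where the printed rates are right. Adding 35 escalation patients gives 150, the top of the stated overall range. This stands: sizes above 15 are permitted, not planned. It does not remove the problem, because Protocol 5.2 says actual enrolment may vary and sets no cap for either NET arm.

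The second reply is that nothing formal hangs on the rule. It says the effect may be considered positive, Protocol 10.3 and SAP 7.6 exclude formal hypothesis testing, and SAP 16.2 has no count threshold. It reports Kaplan-Meier probabilities with 80% and 95% intervals, which reflect the actual n. This also stands and limits the consequence. A reader might infer that type I error control is lost; there is no controlled type I error here to lose.

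Two other stronger readings are tempting:
- At 6 of 18 the exact 80% lower limit is 18.5%, below the 19% lower rate, whereas at 6 of 15 it is 22.6%. A reader might infer that the positive call then breaks the protocol's own criterion. No section makes the lower limit a condition of a positive call; 10.1 gives the limits as additional information for 15 patients.
- Arm A's endpoint definition refers to PFS-evaluable patients, a set defined in neither Protocol 10.2 nor SAP section 6. A reader might infer that every arm's rule rests on that set. The term appears only in the Arm A definition; the count rules speak of evaluable patients. What evaluable means still needs stating for the fix to work.

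**Conclusion.** Protocol 10.1 is wrong as written, to a minor-to-moderate degree. The NET rates of 84.9% and 4.9% belong to exactly 15 evaluable patients with known 11-month status, not to 15 or more. With the count held at 6, the false-positive rate passes 5% with the first extra patient and reaches 11.0% at 18, where the true-positive rate is 95.2%. BTC and the five STS subtypes share the wording but lack the explicit permission to add patients.

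The figures assume independent patients and complete landmark status. How far any arm will exceed its minimum is unknown. The consequence is a looser positive call reported with the wrong error rates, in a descriptive study whose interval estimates would still be correct.

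**What to change.** In Protocol 10.1, or as an entry in SAP 4.4, tie the quoted rates to exactly 30, 15, 15 and 10 evaluable patients, and state one rule for larger cohorts.

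Preferred rule: apply the count to the first 30, 15, 15 or 10 evaluable expansion patients in enrolment order (10 per STS subtype). Define evaluable as landmark status known, and exclude pooled escalation patients from the count. The Kaplan-Meier summary still uses all treated patients. Report how many patients were passed over for unknown status: early progressors always have known status and early-censored patients do not, so heavy early censoring would push the count down.

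Alternative: use the rescaled counts in step 4 of the working and quote the rates for the actual n.

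The two methods can disagree, so adopt only one, on design grounds. SAP 5.2 records that pNET and epNET efficacy was already analysed at the 30JUN2020 cut-off; the entry should say so.

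Cost: a few lines of text and no new data. Under the preferred rule the extra patients do not inform the positive call. Under rescaling, power falls just above the minimum, to 77.3% for a NET arm of 16.
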